9.4.3. Secondary Endpoint(s)

The secondary endpoint(s) of the study are:

- Change in KCCQ-CSS from baseline to Week 12 and Week 24
- Proportion of patients with ≥ 1 class improvement in NYHA Functional Class from baseline to Week 12 and Week 24
- Change in post-Valsalva LVOT-G from baseline to Week 12 and Week 24
- Proportion of patients with post-Valsalva LVOT-G < 30 mmHg at Week 12 and Week 24
- Duration of eligibility for septal reduction therapy (SRT) during the 24-week treatment period in patients who were eligible for SRT at baseline. Participants are classified as being SRT eligible if they have NYHA Class ≥ 3 AND resting or Valsalva LVOT-G ≥ 50 mmHg.
- Change in total workload during CPET from baseline to Week 24

Change in KCCQ-CSS and change in post-Valsalva LVOT-G from baseline to Week 12 and Week 24 will be analyzed using a mixed model repeated measures (MMRM) model with baseline as covariate, randomization stratification factors, visit, treatment group, and interaction terms of treatment by visit and baseline by visit. An unstructured covariance matrix will be specified.

Proportion of patients with ≥ 1 class improvement in NYHA Functional Class from baseline to Week 12 and Week 24 or proportion of patients with post-Valsalva LVOT-G < 30 mmHg at Week 12 and Week 24 will be analyzed using Cochran–Mantel–Haenszel (CMH) test stratified by randomization factors. Patient's Week 20 NYHA Functional Class will be used when Week 24 NYHA Functional Class is not available. Total duration of SRT eligibility (NYHA Class ≥ 3 AND resting or Valsalva LVOT-G ≥ 50 mmHg) during the 24-week treatment period will be analyzed using an ANCOVA model with treatment group and randomization stratification factor beta blocker use/no use as fixed effects adjusting for significant baseline characteristics. The p-value and 95% CI will be obtained using exact method. Adjustment of multiplicity of the primary and secondary endpoints is specified in [Section 9.4.1.1](#).

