7.4. Planned Covariates

Baseline covariates include but are not limited to the stratification factors and baseline measurements. For CPET related endpoints, covariates age, sex, baseline weight will also be evaluated. See [Section 7.7.4](#) for details evaluating covariates effect in the primary endpoint.

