7.5. Subgroup Analyses

Subgroup analyses with relatively moderate sample size will be performed to examine the consistency of the observed treatment effect and to gain insight into the effectiveness of aficamten in subpopulations. Analyses of the primary endpoint will be conducted for the following subgroups:

- Sex (male, female)
- Age group (< 65, ≥ 65 years old)
- Baseline body mass index (<30 vs. ≥ 30)
- Baseline NYHA Class (II, III)
- Baseline KCCQ CSS (≤ median and > median)
- Baseline LVEF (≤ median and > median)
- Baseline N-terminal prohormone brain natriuretic (NT-proBNP) (≤ median and > median)

- CPET modality (treadmill, bicycle)
- Baseline pVO₂ (\leq median, $>$ median)
- Beta Blocker (use, no use)
- Baseline resting LVOT (\leq median and $>$ median)
- Sarcomeric gene mutation status (pathogenic or variant of uncertain significance, and non-disease causing or none)

Subgroup analysis will be performed by including the subgroup effect and subgroup by treatment interaction to the model. The subgroup analysis will be performed based on the imputed dataset generated for the primary analysis of the endpoint if the primary analysis is based on multiple imputation.

In addition, subgroup of IND site status (IND sites vs. non-IND sites) analysis will be performed for the primary estimand, proportion of patients with >1 NYHA functional class improvement, KCCQ CSS change from baseline, post-Valsalva LVOT-G change from baseline at Week 24 and overall adverse events summary to demonstrate compliance with relevant aspects of 21 CFR 312.120.

Analyses on the primary and secondary endpoints in patients who were SRT eligible at baseline may be explored.

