Step 4	The null hypothesis for the third secondary endpoint is that there is no treatment difference in change from baseline to Week 24 in post-Valsalva LVOT-G in the FAS. The hypotheses will be tested at the two-sided significance level of 0.05. If this hypothesis is rejected, testing will proceed to Step 5; otherwise testing will stop.
Step 5	The null hypothesis for the fourth secondary endpoint is that there is no treatment difference in the proportion of patients with post-Valsalva LVOT-G < 30 mmHg at Week 24 in the FAS. The hypotheses will be tested at the two-sided significance level of 0.05. If this hypothesis is rejected, testing will proceed to Step 6; otherwise testing will stop.
Step 6	The null hypothesis for the fifth secondary endpoint is that there is no treatment difference in duration for SRT eligible during the 24-Week treatment period in patients who were SRT eligible at baseline in the FAS. The hypothesis will be tested at the two-sided significance level of 0.05. If this hypothesis is rejected, testing will proceed to Step 7; otherwise testing will stop.
Step 7	The null hypothesis for the sixth secondary endpoint is that there is no treatment difference in the change from baseline to Week 12 in KCCQ-CSS in the FAS. The hypothesis will be tested at the two-sided significance level of 0.05. If this hypothesis is rejected, testing will proceed to Step 8; otherwise testing will stop.
Step 8	The null hypothesis for the seventh secondary endpoint is that there is no treatment difference in proportion of patients with ≥ 1 NYHA functional class improvement at Week 12 in the FAS. The hypotheses will be tested at the two-sided significance level of 0.05. If this hypothesis is rejected, testing will proceed to Step 9; otherwise testing will stop.
Step 9	The null hypothesis for the eighth secondary endpoint is that there is no treatment difference in change from baseline to Week 12 in post-Valsalva LVOT-G in the FAS. The hypotheses will be tested at the two-sided significance level of 0.05. If this hypothesis is rejected, testing will proceed to Step 10; otherwise testing will stop.

Step 10	The null hypothesis for the ninth secondary endpoint is that there is no treatment difference in the proportion of patients with post-Valsalva LVOT-G < 30 mmHg at Week 12 in the FAS. The hypotheses will be tested at the two-sided significance level of 0.05. If this hypothesis is rejected, testing will proceed to Step 11; otherwise testing will stop.

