7.7.4. Supportive Analyses for the Primary Endpoint

To explain heterogeneity or identify treatment effect modifiers from the baseline characteristics, covariates used to define pre-specified subgroups and these covariates by treatment interaction

terms will be included in the ANCOVA model as supportive analysis. Global test of covariates by treatment interactions will be performed.

Stepwise model selection method will be used based on the stay or entry level of 0.05 to evaluate significant baseline covariates impact on the primary endpoint. ANCOVA model will be repeated by adjusting for the significant baseline covariates. Covariates measured as continuous will be introduced to the model as continuous variable. These analyses will be based on observed data.

The normality assumptions of the ANCOVA model will be investigated graphically. The scaled residuals will be examined. A supportive analysis will be performed after transforming pVO₂ data into ranks if greater than 5% of patients have an extreme change from baseline value at Week 24. Extreme values in the pooled data are defined as observations outside of Tukey's outer fences, i.e. observations that are less than the 25% quartile – 3 times the inter quartile range or greater than 75% quartile + 3 times the inter quartile range. Ranks will be applied to all changes from baseline data after the imputation step. Baseline data will be ranked separately.

The secondary estimand will be analyzed using the same primary analysis ANCOVA model for the primary estimand. Subgroup analysis for the secondary estimand will be performed using the same ANCOVA model for the subgroup analysis for the primary estimand.

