Patient SRT eligibility will be assigned after data handling in case there are missing NYHA class or LVOT assessments. Intermittent missing NYHA or LVOT will be imputed follows the same imputing method for missing Week 12 or Week 24; e.g., impute Week 16 NYHA if Week 20 NYHA is available or use Week 12 NYHA if Week 20 NYHA is not available. Patient will be treated as SRT eligible if SRT eligibility can't be determined due to the missing NYHA class or LVOT assessments or clinical visits not performed after patient early terminates from the study.

Total duration will be calculated as the number of days patients are SRT eligible, from the date of the randomization until Week 24. Total duration will be 24 weeks if a patient remains SRT eligible at all visits from baseline until Week 24 (regardless of whether a patient is SRT eligible at Week 24 or not). Because the SRT eligibility status of a patient may change during the study conduct, only intervals during which the patient is SRT eligible, will be summed. The start of the interval is the time of randomization (or resumption of SRT eligible status), and the end of the interval is the date prior to the visit when the patient becomes SRT not eligible.

SRT (Y/N) Case #	Week 2	Week 4	Week 6	Week 8	Week 12	Week 16	Week 20	Week 24	Duration SRT Eligible (Weeks)
1	N	Y	Y	Y	N	N	Y	Y	12
2	Y	Y	N	N	Y	N	N	Y	10
3	Y	Y	N	N	N	N	N	N	6
4	Y	Y	N	N	Y	N	Y	N	14
5	Y	Y	N	N	Y	N	Y	Y	14

Total duration of SRT eligibility during the 24 Week of treatment period will be analyzed using an ANCOVA model includes treatment and randomization stratification factor beta blocker use/non-use as fixed effects and significant baseline characteristics as covariates. Stepwise model selection method will be used based on the default stay or entry level of 0.05 to evaluate significant baseline covariates. Sensitivity analysis of the SRT eligible endpoints includes repeating the same ANCOVA analysis the area under the curve calculated using the numeric value assigned to the SRT eligibility at each visit and treatment duration until Week 24, where SRT eligibility is assigned to value of 1 and SRT not eligible is assigned to value of 0.

- Change in total workload during CPET from baseline to Week 24

The primary and sensitivity analysis for the total workload will follow the same analysis approach for the primary estimand of the primary endpoint.

Subgroup analysis will be performed similarly as specified for the primary endpoint.

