Total duration of SRT eligible during the 24-week of treatment period	Total duration of SRT eligible during the 24-week of treatment period will be analyzed using an ANCOVA model includes treatment and randomization stratification factor beta blocker use/non-use as fixed effects and significant baseline characteristics as covariates. Stepwise model selection method will be used based on the default stay or entry level of 0.05 to evaluate significant baseline covariates.	SRT eligible will be assigned value of 1 and SRT not eligible will be assigned value of 0. Area under the curve using the numeric value assigned and treatment duration until Week 24 will be calculated. AUC will be analyzed using the same ANCOVA model. Same ANCOVA model will be used to analyze the total time for SRT eligibility.	
Change in total workload during CPET from baseline to Week 24	Missing data will be imputed using multiple imputation method (Section 7.7.1). Complete dataset will be analyzed using an ANCOVA model with fixed effects of treatment, randomization stratification factors baseline total workload value and baseline body weight.	Sensitivity analysis 
 • ANCOVA model will be repeated with missing data from subjects who discontinued aficamten treatment as if the aficamten subjects were in the placebo arm. • Tipping point analysis Subgroup analyses for variables in Section 7.5	

¹See [Table 5](#) for details on the two estimands for the primary endpoint.

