where trtid is assigned as 0 at baseline, 0 for placebo group at Week 24 and 1 for active group at Week 24. &c1 and &c2 are the proportion of patients evaluated in each stratification level among all the patients.

Subgroup analysis for the primary endpoint

```
proc mianalyze parms=mixparms covb(effectvar=rowcol)=mixcovb;  
  class <treatment arm> <beta blocker use> <exercise modality> <subgroup> ;  
  =<base pvo2 > <base weight> <treatment arm> <beta blocker use> <Exercise modality>  
  modeleffects Intercept <base pvo2 > <base weight> <treatment arm> <beta blocker use>  
  <Exercise Modality> <subgroup>*<treatment arm>;  
run;
```

SAS codes to evaluate normality assumption for the primary endpoint

The normality assumptions for the ANCOVA analysis will be assessed by residual illustration. The outpred option in the above code stores residuals which are used to test the assumption of normality. Examination of residuals can be done using the following codes.

```
proc univariate data=work normal;  
var ScaledResid; QQPLOT ScaledResid;  
ods output QQPlot=qqplot;  
run;
```

SAS codes to perform CMH test

```
proc freq data=work;  
  tables <Beta blocker use>*<CPET modality>*<treatment arm>*<response Y/N>/CMH  
  exactcmh;  
  exact riskdiff (column=2) relrisk (column=2) commor.  
Run;  
where response is coded as Y=1, N=0.
```

SAS codes to rank observation

```
proc rank data=work out=rwork nplus1;  
Var chg;  
Ranks rchg;  
Run;
```

SAS code for proportional hazard Cox regression model

```
Proc phreg data=work;  
  Class <treatment arm>(ref=first) ;  
  Model <time>*< censor (1)>= ;  
  Strata <beta blocker use> <CPET modality> ;  
Run;
```

SAS code for stratified logistics regression model

```
Proc phreg data=work;  
  Class <treatment arm>;  
  Model <Response> (event='Y')= <treatment arm> <baseline covariates>/selection=stepwise  
  details;  
  Strata <beta blocker use> ;  
Run;
```

SAS code for EQ-5D-5L Index Value

```
*****  
*SAS syntax code for the computation of index*  
*values with the US TTO value set*  
*****  
  
data WORK.CAT;  
set WORK.CAT;  
  
if mobility eq 1 then disut_mo=0;  
else if mobility eq 2 then disut_mo=0.096;  
else if mobility eq 3 then disut_mo=0.122;  
else if mobility eq 4 then disut_mo=0.237;  
else if mobility eq 5 then disut_mo=0.322;  
  
if selfcare eq 1 then disut_sc=0;  
else if selfcare eq 2 then disut_sc=0.089;  
else if selfcare eq 3 then disut_sc=0.107;  
else if selfcare eq 4 then disut_sc=0.220;  

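### Step 6 (duration of SRT eligibility) picks its covariates stepwise on its own outcome, with no candidate list and no stated role for treatment, so the 0.05 level is not assured

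*SAP*

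**What the plan says.** SAP 7.6 claims control of the overall type I error at two-sided 0.05 across the primary and secondary endpoints, tested in a fixed order. Step 6 in SAP Table 4 concerns "duration for SRT eligible during the 24-Week treatment period in patients who were SRT eligible at baseline in the FAS". It is tested at 0.05; rejection opens Step 7, and failure stops the sequence.

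SAP 7.8.1 analyses this endpoint by ANCOVA with treatment and beta-blocker use as fixed effects, plus the baseline characteristics found to be significant. The rule for finding them is: "Stepwise model selection method will be used based on the default stay or entry level of 0.05 to evaluate significant baseline covariates". Table 6 lists this as the primary analysis method. Protocol 9.4.3 gives no list and no selection rule, only "beta blocker use/no use as fixed effects adjusting for significant baseline characteristics".

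Three other places bear on the point:

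- SAP 7.4, the general statement on covariates, leaves the set open: "Baseline covariates include but are not limited to the stratification factors and baseline measurements".
- In Table 6 the sensitivity analysis on the area under the curve keeps the same model: "AUC will be analyzed using the same ANCOVA model".
- The only stepwise code in SAP 11.5 belongs to a stratified logistic model. It puts treatment in the same statement as the covariates, "<treatment arm> <baseline covariates>/selection=stepwise", with no option forcing treatment in. There is no code for the Step 6 ANCOVA.

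**The concern.** Step 6 is the only one of the 11 steps whose covariates are chosen by their association with its own outcome. pVO2 and total workload have named covariates. KCCQ-CSS and post-Valsalva LVOT-G have a specified MMRM, whose conditional region terms depend on baseline data only. The responder endpoints use a CMH test stratified by the randomization factors. For the primary endpoint the SAP does the reverse of Step 6: covariates are fixed in 7.7.1, and stepwise selection "based on the stay or entry level of 0.05 to evaluate significant baseline covariates impact on the primary endpoint" appears only among the supportive analyses in 7.7.4.

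Two things are at stake. First, the model behind a confirmatory claim is not known until the outcome data are seen, and no fixed-covariate analysis of duration is planned as a check. Second, the error rate depends on an unstated choice.

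- **Selection ignoring treatment.** Under the null, randomization makes treatment independent of the outcome and covariates that drive selection, so the later treatment test keeps close to its level.
- **Treatment held in.** Selection favours covariates that happen to shrink the within-arm residual. The standard error becomes too small, with no matching shrinkage of the treatment difference, and the test rejects too often.

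A false pass at Step 6 would also open five further tests.

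**Working it through.** **The plan's own figures.** The only computed design figure concerns the primary endpoint: difference 1.5, SD 3.5, 270 randomized, 10% missing (SAP 3.3.1). Per arm, n = 2(1.96 + 1.2816)² × 3.5² / 1.5² = 114.4, so 115. In total 230 / 0.9 = 255.6, so 256. With 135 × 0.9 = 121.5 evaluable per arm, power is 91.6%, which reproduces the stated figure of more than 90%. Nothing comparable is given for Step 6. Its only figure is the nominal 0.05, so that is what was tested.

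**Inputs from the documents.** 1:1 allocation; beta-blocker use at about 70% (the cap, taken as the assumed share); entry and stay level 0.05; a duration that cannot exceed 24 weeks.

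**Assumptions, because the documents are silent.** 40, 60, 80 or 120 SRT-eligible patients, and 10 or 20 candidates. Ten comes from SAP 7.5 ("Analyses of the primary endpoint will be conducted for the following subgroups"), which lists 12 variables. Remove beta-blocker use, already in the model, and baseline NYHA, essentially constant at Class III in this subgroup: 12 − 2 = 10. The SAP does not tie that list to Step 6.

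**How often the model changes by chance.** If no candidate is prognostic and candidates are independent, the chance that at least one enters is roughly 1 − 0.95¹⁰ = 40% with 10 candidates and 1 − 0.95²⁰ = 64% with 20.

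**Type I error under no treatment effect.** Main run: 6000 trials per cell, outcome bounded at 2 to 24 weeks, independent candidates, Monte Carlo SE √(0.05 × 0.95 / 6000) = 0.3 points. The range columns add repeat runs of 4000 to 15,000 trials per cell, some with prognostic or correlated candidates.

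Treatment held in during selection:

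| Eligible patients | 10 candidates, main run | 10, range over runs | 20 candidates, main run | 20, range over runs |
|---|---|---|---|---|
| 40 | 6.5% | 6.5–7.6% | 9.0% | 9.0–10.5% |
| 60 | 6.1% | 5.8–7.0% | 7.6% | 7.2–8.3% |
| 80 | 5.5% | 5.5–6.1% | 6.4% | 6.4–7.1% |
| 120 | 5.6% | 5.1–5.7% | 6.1% | one value |

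Other rules in the main run, over all cells:

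- selection ignoring treatment, which is then added: 4.8–5.3%
- treatment as an ordinary candidate: 4.9–5.8%
- two fixed covariates: 4.8–5.5%

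**Stress case.** A separate set (outcome bounded at 0 to 24 weeks, 6000 trials per cell, 30 candidates, none or two prognostic) gave, with treatment held in, 11.6–12.9% (n=40), 9.1–9.4% (n=60), 7.4% (n=80) and 6.1–7.2% (n=120). In that set, over 12 and 30 candidates, selection without treatment gave 4.6–5.7%, and treatment plus beta-blocker use alone gave 4.7–5.7%.

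**The case against.** The best case against has four parts.

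1. **Size.** With the 10 candidates the documents suggest, the excess is small. A run of 15,000 trials per cell (SE about 0.18 points) gave 5.8%, 6.1% and 5.7% at 60, 80 and 120 patients with treatment held in, against 4.8%, 5.4% and 5.2% without it. The 9.0% figure needs 40 patients and 20 candidates, neither of which is in the documents. At 80 to 120 patients with 10 candidates, the held-in results overlap those for treatment as an ordinary candidate. This stands: the excess is modest unless the subgroup is small or the list long.
2. **Remote null.** Step 6 is reached only after NYHA improvement and both post-Valsalva LVOT-G endpoints at Week 24 are rejected, and SRT eligibility is built from NYHA class and LVOT-G. No effect on duration is then unlikely. This stands as a practical point. It does not remove the need, because the plan claims control without that condition and Step 6 tests a subgroup.
3. **Timing.** SAP 1 says decisions on the final analysis precede database lock, and SAP 4.2 places unblinding after lock. If the covariates were chosen before lock, treatment could not take part. But SAP 1 names no covariates and may mean only that the SAP is final by then.
4. **Context.** SAP 7.4 and 7.5 are not written for Step 6, so the accurate statement is that Step 6 has no list. SAP 7.9.1 does plan selection-free analyses of related SRT endpoints (CMH at Week 24 and Kaplan-Meier for first ineligibility), but not of duration. A Class IV baseline is not strictly excluded, because NYHA is reassessed on Day 1. None of this alters the conclusion.

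**Conclusion.** The concern holds. A confirmatory test that gates five others uses covariates selected on the trial's own outcome, from a set that is not listed, under a rule that does not say how treatment is handled. Treatment is a stated fixed effect of the final model, so holding it in during selection is a natural reading, and that is the reading that inflates the error. The range over all runs is 5.1–7.6% with 10 candidates and 6.1–10.5% with 20, for 40 to 120 eligible patients. Selecting without treatment, or fixing the covariates, keeps the level near 5%.

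These sizes rest on assumed subgroup and candidate numbers and are largest where the subgroup is small. The issue arises only if Steps 1 to 5 are all rejected, and the primary endpoint is unaffected. The text should be changed, but the defect does not undermine the trial.

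**What to change.** In SAP 7.8.1, SAP Table 6, protocol 9.4.3 and both synopses, replace the stepwise rule with covariates named before unblinding: treatment, beta-blocker use and one or two baseline values already collected. Baseline post-Valsalva LVOT-G and KCCQ-CSS are examples; baseline NYHA would add almost nothing in this subgroup. Keep the stepwise model as a supportive analysis, as SAP 7.7.4 does for the primary endpoint.

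The minimum alternative, which also restores the level in the simulations, is to close the candidate list and state that selection is run without treatment in the model, with treatment added afterwards. Adding CPET modality is optional and is not the source of the inflation.

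The cost is SAP and protocol wording. Some precision is lost if a strong predictor is not named.

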7.9. Analysis of the Exploratory Efficacy Endpoints

Exploratory endpoints are specified in [Section 2.2.3](#). Other echocardiography parameters and CPET parameters not listed as secondary endpoints or in [Section 2.2.3](#) may also be analyzed as exploratory endpoints. All 10 summary scores will be derived for KCCQ. Change from baseline in each summary scores (except CSS) to Weeks 12 and 24 will be analyzed as exploratory endpoints. Patients with ≥ 5 , 10 and 20 points improvement in KCCQ summary scores at Weeks 12 and 24 will also be summarized and analyzed. Domain scores and summary score of SAQ-7 will be derived. Health state for EQ-5D-5L and index value using US value set will be calculated. Analysis of change from baseline in index score and VAS score of EQ-5D-5L be performed. Proportional change in Valsalva and resting LVOT-G will be derived and analyzed as exploratory endpoints.

